10.4 Time to Progression

Time to Progression (TTP) is defined as the duration of time from start of treatment to time of disease progression as defined in section 10.1. Death from any cause or initiation of a new anti-neoplastic therapy will also be considered a progression event.

10.5 Time to Next Therapy

Time to Next Therapy (TNT) is defined as the duration from start of protocol treatment to time of initiation of any new anti-neoplastic therapy, including radiation or intrathecal therapy.

11. ADVERSE EVENT REPORTING REQUIREMENTS

11.1 Definitions

11.1.1 Adverse Event (AE) Definition

Adverse event (AE) means any untoward medical occurrence in a patient or subject administered a pharmaceutical product; the untoward medical occurrence does not necessarily have a causal relationship with this treatment. An AE can therefore be any unfavorable and unintended sign (including an abnormal laboratory finding), symptom, or disease temporally associated with the use of a medicinal (investigational) product whether or not it is related to the medicinal product. This includes any newly occurring event, or a previous condition that has increased in severity or frequency since the administration of study drug.

An abnormal laboratory value will not be assessed as an AE unless that value leads to discontinuation or delay in treatment, dose modification, therapeutic intervention, or is considered by the investigator to be a clinically significant change from baseline.

CONFIDENTIAL

This document is confidential. Do not disclose or use except as authorized.

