1.2 Primary Objectives

- To evaluate the rate of very good partial response (VGPR) or better to IDR in patients with untreated WM
- To evaluate the toxicity profile of IDR in patients with untreated WM

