2.1.2.4 Hematologic Events

In clinical trials, Grade 3 and 4 cytopenias were reported in 48% of patients treated with rituximab; these include: lymphopenia (40%), neutropenia (6%), leukopenia (4%), anemia (3%), and thrombocytopenia (2%). The median duration of lymphopenia was 14 days (range, 1 to 588 days) and of neutropenia was 13 days (range, 2 to 116 days). A single occurrence of transient aplastic anemia (pure red cell aplasia) and two occurrences of hemolytic anemia following rituximab therapy were reported.

In addition, there have been a limited number of post marketing reports of prolonged pancytopenia, marrow hypoplasia, and late onset neutropenia (defined as occurring 40 days after the last dose of rituximab) in patients with hematologic malignancies. In reported cases of late onset neutropenia (NCI-CTC Grade 3 and 4), the median duration of neutropenia was 10 days (range 3 to 148 days). Documented resolution of the neutropenia was described in approximately one-half of the reported cases; of those with documented recovery, approximately half received

CONFIDENTIAL

This document is confidential. Do not disclose or use except as authorized.

growth factor support. In the remaining cases, information on resolution was not provided. More than half of the reported cases of delayed onset neutropenia occurred in patients who had undergone prior autologous bone marrow transplantation. In an adequately designed, controlled, clinical trial, the reported incidence of NCI-CTC Grade 3 and 4 neutropenia was higher in patients receiving rituximab in combination with fludarabine as compared to those receiving fludarabine alone (76% [39/51] vs. 39% [21/53]).

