6.2.1.1 Dose Reductions for Hematologic Toxicities

Dosage adjustments for hematologic toxicity are outlined in Table 6-2.

**Table 6-2 Ixazomib Dose Adjustments for Hematologic Toxicities
Ixazomib can be held for maximum of 28 days except at discretion of PI**

Criteria	Action
Within-Cycle Dose Modifications	
If platelet count $\leq 30 \times 10^9/\text{L}$ or ANC $\leq 0.50 \times 10^9/\text{L}$ on a ixazomib dosing day (other than Day 1)	Ixazomib dose should be withheld. Complete blood count (CBC) with differential should be repeated at least every other day until the ANC and/or platelet counts have exceeded the prespecified values (see Section 6.2.1) on at least 2 occasions. Upon recovery, ixazomib may be reinitiated with 1 dose level reduction.

CONFIDENTIAL

This document is confidential. Do not disclose or use except as authorized.

Dosage adjustments for hematologic toxicity are outlined in Table 6-2.

Table 6-2 Ixazomib Dose Adjustments for Hematologic Toxicities
Ixazomib can be held for maximum of 28 days except at discretion of PI

Criteria	Action
Dose Modifications for Subsequent Treatment Cycles	
Delay of > 2 weeks in the start of a subsequent cycle due to lack of toxicity recovery as defined in Section 6.3.1.	Hold ixazomib until resolution as per criteria Section 6.2. Upon recovery, reduce ixazomib 1 dose level.
ANC < 1.0 × 10 ⁹ /L, platelet count < 75 × 10 ⁹ /L, or other nonhematologic toxicities > Grade 1 or not to the patient’s baseline condition	The maximum delay before treatment should be discontinued will be 28 days or at the discretion of the PI.
Dose Modifications for Subsequent Treatment Cycles	
All hematologic toxicities	For hematologic toxicity that occurs during a cycle but recover in time for the start of the next cycle,: If dose was reduced within the cycle, start the next cycle at that same dose. If due to toxicity timing, ie, after Day 15 dosing thus a dose reduction was not required at that point in the cycle, reduce ixazomib by 1 dose level at the start of that cycle. Do not reduce the dose both within a cycle and at the start of the cycle for the same most severe toxicity.

6.2.1.2Dose Reductions for Non-Hematologic Toxicities

CONFIDENTIAL

This document is confidential. Do not disclose or use except as authorized.

Table 6-3 Ixazomib Treatment Modification (Delays, Reductions, and Discontinuations) Due to Adverse Events (Non-Hematologic Toxicities)

Ixazomib can be held for maximum of 28 days except at discretion of PI

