11.1.2 Serious adverse event (SAE) Definition

Serious AE (SAE) means any untoward medical occurrence that at any dose:

- Results in **death**.
- Is **life-threatening** (refers to an AE in which the patient was at risk of death at the time of the event. It does not refer to an event which hypothetically might have caused death if it were more severe).
- Requires inpatient **hospitalization or prolongation of an existing hospitalization** (see clarification in the paragraph below on planned hospitalizations).
- Results in **persistent or significant disability or incapacity**. (Disability is defined as a substantial disruption of a person's ability to conduct normal life functions).
- Is a **congenital anomaly/birth defect**.
- Is a **medically important event**. This refers to an AE that may not result in death, be immediately life threatening, or require hospitalization, but may be considered serious when, based on appropriate medical judgment, may jeopardize the patient, require medical or surgical intervention to prevent 1 of the outcomes listed above, or involves suspected transmission via a medicinal product of an infectious agent. Examples of such medical events include allergic bronchospasm requiring intensive treatment in an emergency room or at home, blood dyscrasias or convulsions that do not result in inpatient hospitalization, or the development of drug dependency or drug abuse; any organism, virus, or infectious particle (eg, prion protein transmitting Transmissible Spongiform Encephalopathy), pathogenic or nonpathogenic, is considered an infectious agent.

Clarification should be made between a serious AE (SAE) and an AE that is considered severe in intensity (Grade 3 or 4), because the terms serious and severe are NOT synonymous. The general term severe is often used to describe the intensity (severity) of a specific event; the event itself, however, may be of relatively minor medical significance (such as a Grade 3 headache). This is NOT the same as serious, which is based on patient/event outcome or action criteria described above, and is usually associated with events that pose a threat to a patient's life or ability to function. A severe AE (Grade 3 or 4) does not necessarily need to be considered serious. For example, a white blood cell count of 1000/mm³ to less than 2000 is considered Grade 3 (severe) but may not be considered serious. Seriousness (not intensity) serves as a guide for defining regulatory reporting obligations.

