11.2 Procedures for AE and SAE Recording and Reporting

AEs may be spontaneously reported by the patient and/or in response to an open question from study personnel or revealed by observation, physical examination, or other diagnostic procedures. Any clinically relevant deterioration in laboratory assessments or other clinical finding is considered an AE. When possible, signs and symptoms indicating a common underlying pathology should be noted as one comprehensive event. For serious AEs, the investigator must determine both the intensity of the event and the relationship of the event to study drug administration. For serious pretreatment events, the investigator must determine both the intensity of the event and the relationship of the event to study procedures.

AEs which are serious must be reported to Millennium Pharmacovigilance (or designee) from the first dose of study drug through 30 days after administration of the last dose of ixazomib. Any SAE that occurs at any time after completion of **ixazomib** treatment or after the designated follow-up period that the sponsor-investigator and/or sub-investigator considers to be related to any study drug must be reported to Millennium Pharmacovigilance (or designee). In addition, new primary malignancies that occur during the follow-up periods must be reported, regardless of causality to study regimen, for a minimum of three years after the last dose of the investigational product, starting from the first dose of study drug. All new cases of primary malignancy must be reported to Millennium Pharmacovigilance (or designee).

CONFIDENTIAL

This document is confidential. Do not disclose or use except as authorized.

Planned hospital admissions or surgical procedures for an illness or disease that existed before the patient was enrolled in the trial are not to be considered AEs unless the condition deteriorated in an unexpected manner during the trial (e.g., surgery was performed earlier or later than planned). All SAEs should be monitored until they are resolved or are clearly determined to be due to a patient's stable or chronic condition or intercurrent illness(es).

Since this is an investigator-initiated study, the principal investigator [name], also referred to as the sponsor-investigator, is responsible for reporting serious adverse events (SAEs) to any regulatory agency and to the sponsor- investigator's EC or IRB.

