14.6 Safety Analysis

Safety evaluations will be presented by escalating dose and based on the incidence, intensity and type of adverse events (AEs).

All AEs occurring on study will be listed in by-participant data listings. A by-dose tabulation will be provided that enumerates AEs by maximum severity. Deaths, SAEs and events resulting in study discontinuation will be tabulated.

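### Safety tables built on AEs alone may under-count graded cytopenias that trigger no action, lymphopenia above all, although toxicity is a primary objective

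*Combined protocol and SAP*

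**What the plan says.** Section 1.2 lists as a primary objective "To evaluate the toxicity profile of IDR in patients with untreated WM". Section 14.6 says that safety evaluations are "based on the incidence, intensity and type of adverse events (AEs"), with a tabulation by maximum severity. Section 14 plans no summary of graded laboratory values.

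Two rules decide when a laboratory finding becomes an AE.

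- Section 11.1.1: "An abnormal laboratory value will not be assessed as an AE unless that value leads to discontinuation or delay in treatment, dose modification", or leads to "therapeutic intervention, or is considered by the investigator to be a clinically significant change from baseline".
- Section 11.2: "Any clinically relevant deterioration in laboratory assessments or other clinical finding is considered an AE". This rule requires no action, but it still rests on a judgement of relevance.

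The haematologic action thresholds in section 6.2.1 and Table 6-2 (dose adjustments) name only ANC and platelets. Section 2.1.2.4 cites Grade 3-4 cytopenias in 48% of rituximab-treated patients, with lymphopenia the most frequent at 40%. The study calendar schedules CBC with differential and serum chemistry throughout treatment.

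**The concern.** A single-arm trial with a descriptive toxicity objective needs severe cytopenia rates that can be read against other regimens. Here a count reaches the safety tables only if it prompted an action or treatment, or if someone judged it significant or relevant. The reported rate therefore depends partly on dosing rules and on investigator habit, and no planned table shows the counts themselves.

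Lymphocytes are the clearest case. They carry the highest cytopenia rate that the protocol cites for rituximab, yet no dosing rule names them, so they enter the tables mainly through judgement. The calendar adds to the exposure: it draws blood on induction Days 8 and 15 but marks adverse event evaluation only on Day 1 of each cycle.

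**Working it through.** **1. Which values reach the AE tables without a judgement.** Section 6.2.1 and Table 6-2 set beside 11.1.1 (counts in x10^9/L):

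| Value | Protocol action | Route to the AE tables |
|---|---|---|
| ANC <1.0 or platelets <75 on Day 1 | cycle delayed | counted |
| ANC ≤0.50 or platelets ≤30 on a later dosing day | dose withheld | counted |
| ANC >0.50 and <1.0, or platelets >30 and <75, on Day 8 or 15 | no hold on the day | treatment or judgement, or possibly the row of Table 6-2 for all haematologic toxicities |
| Lymphocytes, total white cells | no threshold named | treatment or judgement, or possibly that same row |

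**2. Where the mid-cycle gap lies.** Calendar footnote 8 drops the Day 8 and 15 safety laboratories in induction cycles 4-6 and in all maintenance cycles. That leaves 3 cycles x 2 days = 6 scheduled draws per patient. In the later cycles the scheduled draws fall on Day 1, where a low ANC or platelet count delays the cycle and so counts.

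**3. The plan's own safety figure.** Section 14.1 gives a 93% probability of seeing at least one event of true probability 10% in 26 participants. Check: 1 - 0.9^26 = 0.9354, which agrees. The formula assumes that every event is recorded.

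**4. Patients exposed to the filter.** Inputs: n = 26 (section 14.1: 27 accrued, one of whom never started) and p = 0.40 (section 2.1.2.4). Expected number: 26 x 0.40 = 10.4. The 5th and 95th percentiles of Binomial(26, 0.40) are 6 and 15.

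**5. What the unknown share does.** Let c be the share of such events that are recorded as AEs. The documents do not give c, so the values below are assumptions. Lymphopenia cases counted = 26 x 0.40 x c. For a laboratory event of true probability 10%, P(at least one counted) = 1 - (1 - 0.10c)^26.

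| c | Lymphopenia cases counted | P(at least one), 10% event |
|---|---|---|
| 1 | 10.4 | 0.94 |
| 0.75 | 7.8 | 0.87 |
| 0.50 | 5.2 | 0.74 |
| 0.25 | 2.6 | 0.48 |
| 0 | 0 | 0 |

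**The case against.** A reader might infer that these cytopenias vanish from the tables. The documents do not support that, for four reasons.

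- Values that delay, withhold or reduce treatment count as AEs. So do those treated with growth factor or transfusion, which sections 5.3.2 and 6.1.3 permit, and any the investigator finds significant. Section 11.2 reaches any clinically relevant deterioration without requiring an action.
- Section 11.1.2 takes a white count of 1000 to below 2000 as its illustration of a severe AE. It says that such a count "is considered Grade 3 (severe) but may not be considered serious". That suggests the authors expected it to be recorded.
- Table 6-2 also has a row for all haematologic toxicities. It orders a one-level reduction at the next cycle when timing, such as after Day 15 dosing, meant that none was required earlier. It gives no grade threshold, and its branches do not clearly reach a Day 8 ANC of 0.6 that recovers by the next Day 1. It does weaken any claim that no protocol action could apply.
- Lymphopenia was recorded as an AE in 20 of 173 patients (12%) in the oral ixazomib combination studies (Table 1-3), so AE reporting does pick it up.

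It is also fair to say that no decision turns on this. The success rule in 14.1 concerns VGPR or better only, and no toxicity threshold is set. The ixazomib data that the protocol cites are AE tables, so AE-based reporting is the like-for-like format there.

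All of this stands, and it limits the claim. It does not remove it. Most of these routes depend on an action or a judgement, 11.1.1 and 11.2 word that judgement differently, and nothing in section 14 shows how often a graded value was left out. Section 6.2.1.5 says toxicities are reported by common toxicity criteria, but that sets the grading scale, not which values are counted.

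**Conclusion.** The plan as written can under-count graded cytopenias that trigger no action. The extent is unknown and depends on the investigator. Lymphopenia and low white count are most exposed. For ANC and platelets the exposure is mainly Days 8 and 15 of induction cycles 1-3.

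About 10 of 26 patients (6 to 15) is the number exposed at the cited lymphopenia rate. A reader might take it as the number lost, but that would require c = 0, which the documents do not show. The 40% comes from rituximab trials, which section 6.1.6 describes as single-agent studies. It may not fit this regimen, in which rituximab starts only at cycle 3. For the same reasons, the documents do not establish that the toxicity result will be biased low or will look better than the cited 48%. The direction of any error is towards under-counting; its size cannot be derived from the plan. The 93% figure in 14.1 is arithmetically sound but holds only for events that are fully recorded.

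**What to change.** In section 14.6 add a table for the Safety Analysis Set giving worst on-treatment CTCAE v4 grade and shift from baseline for ANC, lymphocytes, white cells, haemoglobin, platelets, ALT, AST, bilirubin and creatinine. Derive it from all scheduled laboratory values, whether or not an AE was reported, and present it beside the AE table. State the baseline value, the on-treatment window and the number of patients with post-baseline values. Reconcile sections 11.1.1 and 11.2 so that a single rule says when a laboratory value is an AE. The dosing thresholds need not change for this purpose.

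The cost is modest: no new tests and no change to care. Section 12.1.2 lists no laboratory form, however, so values for about 26 patients may have to be extracted from source records. Reported Grade 3-4 laboratory rates will be higher than the AE table alone would show. Nadirs in cycles without Day 8 and 15 laboratories will still be missed, and a footnote to the table should say so.

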11.1.2 Serious adverse event (SAE) Definition

Serious AE (SAE) means any untoward medical occurrence that at any dose:

- Results in **death**.
- Is **life-threatening** (refers to an AE in which the patient was at risk of death at the time of the event. It does not refer to an event which hypothetically might have caused death if it were more severe).
- Requires inpatient **hospitalization or prolongation of an existing hospitalization** (see clarification in the paragraph below on planned hospitalizations).
- Results in **persistent or significant disability or incapacity**. (Disability is defined as a substantial disruption of a person's ability to conduct normal life functions).
- Is a **congenital anomaly/birth defect**.
- Is a **medically important event**. This refers to an AE that may not result in death, be immediately life threatening, or require hospitalization, but may be considered serious when, based on appropriate medical judgment, may jeopardize the patient, require medical or surgical intervention to prevent 1 of the outcomes listed above, or involves suspected transmission via a medicinal product of an infectious agent. Examples of such medical events include allergic bronchospasm requiring intensive treatment in an emergency room or at home, blood dyscrasias or convulsions that do not result in inpatient hospitalization, or the development of drug dependency or drug abuse; any organism, virus, or infectious particle (eg, prion protein transmitting Transmissible Spongiform Encephalopathy), pathogenic or nonpathogenic, is considered an infectious agent.

Clarification should be made between a serious AE (SAE) and an AE that is considered severe in intensity (Grade 3 or 4), because the terms serious and severe are NOT synonymous. The general term severe is often used to describe the intensity (severity) of a specific event; the event itself, however, may be of relatively minor medical significance (such as a Grade 3 headache). This is NOT the same as serious, which is based on patient/event outcome or action criteria described above, and is usually associated with events that pose a threat to a patient's life or ability to function. A severe AE (Grade 3 or 4) does not necessarily need to be considered serious. For example, a white blood cell count of 1000/mm³ to less than 2000 is considered Grade 3 (severe) but may not be considered serious. Seriousness (not intensity) serves as a guide for defining regulatory reporting obligations.

11.1.3 Expectedness

Adverse events can be "Expected" or "Unexpected."

11.1.3.1 Expected adverse event

Expected adverse events are those that have been previously identified as resulting from administration of the agent. For the purposes of this study, an adverse event is considered

CONFIDENTIAL

This document is confidential. Do not disclose or use except as authorized.

expected when it appears in the current adverse event list, the Investigator's Brochure, the package insert or is included in the informed consent document as a potential risk.

Refer to Section 6.1 for a listing of expected adverse events associated with the study agent(s).

11.1.3.2 Unexpected adverse event

For the purposes of this study, an adverse event is considered unexpected when it varies in nature, intensity or frequency from information provided in the current adverse event list, the Investigator's Brochure, the package insert or when it is not included in the informed consent document as a potential risk.

11.1.4 Attribution

Attribution is the relationship between an adverse event or serious adverse event and the study treatment. Attribution will be assigned as follows:

- Definite – The AE is clearly related to the study treatment.
- Probable – The AE is likely related to the study treatment.
- Possible – The AE may be related to the study treatment.
- Unlikely - The AE is doubtfully related to the study treatment.
- Unrelated - The AE is clearly NOT related to the study treatment.

11.2 Procedures for AE and SAE Recording and Reporting

AEs may be spontaneously reported by the patient and/or in response to an open question from study personnel or revealed by observation, physical examination, or other diagnostic procedures. Any clinically relevant deterioration in laboratory assessments or other clinical finding is considered an AE. When possible, signs and symptoms indicating a common underlying pathology should be noted as one comprehensive event. For serious AEs, the investigator must determine both the intensity of the event and the relationship of the event to study drug administration. For serious pretreatment events, the investigator must determine both the intensity of the event and the relationship of the event to study procedures.

AEs which are serious must be reported to Millennium Pharmacovigilance (or designee) from the first dose of study drug through 30 days after administration of the last dose of ixazomib. Any SAE that occurs at any time after completion of **ixazomib** treatment or after the designated follow-up period that the sponsor-investigator and/or sub-investigator considers to be related to any study drug must be reported to Millennium Pharmacovigilance (or designee). In addition, new primary malignancies that occur during the follow-up periods must be reported, regardless of causality to study regimen, for a minimum of three years after the last dose of the investigational product, starting from the first dose of study drug. All new cases of primary malignancy must be reported to Millennium Pharmacovigilance (or designee).

CONFIDENTIAL

This document is confidential. Do not disclose or use except as authorized.

Planned hospital admissions or surgical procedures for an illness or disease that existed before the patient was enrolled in the trial are not to be considered AEs unless the condition deteriorated in an unexpected manner during the trial (e.g., surgery was performed earlier or later than planned). All SAEs should be monitored until they are resolved or are clearly determined to be due to a patient's stable or chronic condition or intercurrent illness(es).

Since this is an investigator-initiated study, the principal investigator [name], also referred to as the sponsor-investigator, is responsible for reporting serious adverse events (SAEs) to any regulatory agency and to the sponsor- investigator's EC or IRB.

Regardless of expectedness or causality, all SAEs (including serious pretreatment events) must also be reported to Millennium Pharmacovigilance:

Fatal and Life Threatening SAEs within 24 hours of the sponsor-investigator's observation or awareness of the event

All other serious (non-fatal/non life threatening) events within 4 calendar days of the sponsor-investigator's observation or awareness of the event

See below for contact information for the reporting of SAEs to Millennium Pharmacovigilance. The sponsor-investigator must fax or email the SAE Form per the timelines above. A sample of an SAE Form will be provided. The SAE report must include at minimum:

- Event term(s)
- Serious criteria
- Intensity of the event(s): **Sponsor-investigator's or sub-investigator's determination. Intensity for each SAE, including any lab abnormalities, will be determined by using the NCI CTCAE version specified in the protocol, as a guideline, whenever possible. The criteria are available online at <http://ctep.cancer.gov/reporting/ctc.html>.**
- Causality of the event(s): **Sponsor-investigator's or sub-investigator's determination of the relationship of the event(s) to study drug administration.**

Follow-up information on the SAE may be requested by Millennium.

Intensity for each SAE, including any lab abnormalities, will be determined by using the NCI CTCAE version used at your institution, as a guideline, whenever possible. The criteria are available online at <http://ctep.cancer.gov/reporting/ctc.html>.

In the event that this is a multisite study, the sponsor-investigator is responsible to ensure that the SAE reports are sent to Millennium Pharmacovigilance (or designee) from all sites participating in the study. Sub-investigators must report all SAEs to the sponsor-investigator so that the sponsor-investigator can meet his/her foregoing reporting obligations to the required regulatory agencies and to Millennium Pharmacovigilance, unless otherwise agreed between the sponsor-investigator and sub-investigator(s).

Relationship to all study drugs for each SAE will be determined by the investigator or sub-

CONFIDENTIAL

This document is confidential. Do not disclose or use except as authorized.

investigator by responding yes or no to the question: Is there a reasonable possibility that the AE is associated with the study drug(s)?

Sponsor-investigator must also provide Millennium Pharmacovigilance with a copy of all communications with applicable regulatory authorities related to the study product(s), as soon as possible but no later than 4 calendar days of such communication.

SAE and Pregnancy Reporting Contact Information

[contact]

Email: [contact]

Suggested Reporting Form:

- SAE Report Form (provided by Millennium)
- US FDA MedWatch 3500A:
<http://www.fda.gov/Safety/MedWatch/HowToReport/DownloadForms/default.htm>

Procedures for Reporting Drug Exposure During Pregnancy and Birth Events

If a woman becomes pregnant or suspects that she is pregnant while participating in this study **or within 90 days after the last dose**, she must inform the investigator immediately and permanently discontinue study drug. The sponsor-investigator must immediately fax a completed Pregnancy Form to the Millennium Department of Pharmacovigilance or designee (see Section 8.2). The pregnancy must be followed for the final pregnancy outcome.

If a female partner of a male patient becomes pregnant during the male patient's participation in this study, the sponsor-investigator must also immediately fax a completed Pregnancy Form to the Millennium Department of Pharmacovigilance or designee (see Section 8.2). Every effort should be made to follow the pregnancy for the final pregnancy outcome.

